	This feasibility study is a prospective, randomized, two-period crossover multi-center study of 2 weeks of home use of Control-IQ 1.5 technology (run-in period), followed by 2 weeks of home use of Control-IQ 2.0 technology at one target, followed by 2 weeks of home use of Control-IQ 2.0 at another target. This automated insulin dosing (AID) system will be evaluated in multiple age groups, with late bolus meal challenges.						
	t:slim X2 insulin pump with Control-IQ technology 1.5 (Run-In Period) t:slim X2 insulin pump with Control-IQ technology 2.0 (Treatment Periods)						
-	The objectives of the study are to assess safety of and explore glycemic outcomes with Control-IQ technology 2.0 in adults, children and preschoolers with type 1 diabetes using different targets and after late bolus meal challenges.						
Number of Sites	Up to 6 clinical sites in the US.						
Study Design	Randomized sequence, prospective safety study						
	Up to 100 participants signing consent to use the study devices, so that at least 72 complete the study (at least 30 participants age 14+, at least 30 participants age 6-13, and at least 12 participants age 2-5), plus local contacts for adult participants. Enrollment goal is at least 50% of all participants in each age group have an HbA1c at baseline of \geq 7.5%.						

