8.1 General Statistical Considerations

Summary statistics will be generated for all relevant variables. In the comparison of continuous variables, distributions will be tested for the normality assumption. If standard parametric techniques are found to be inadequate, an appropriate non-parametric technique will be used. Categorical variables will be presented using frequencies and percentages and compared using differences in proportions unless stated otherwise. For safety/adverse event reporting, both the number of overall events and the number of subjects experiencing that event will be tabulated. No corrections will be made for multiple testing procedures. All analyses will be conducted using SAS® version 9.4 or higher. Although this study features a crossover design, it will be assumed for the exploratory purposes of this analysis that there are no residual period effects and no carryover effects present. The correlated nature of data collected by the same subject across multiple conditions will be accounted for in the statistical modeling, such as using a paired t-test for

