8.6.4 Analysis of Late Bolus Meal Challenges

All analyses in section 8.6.4 will be conducted in the late bolus meal challenge analysis set. Data included in these analyses will be restricted to data during the meal challenge window (start of meal through 5 hours from meal imitation [3 hours for age 2-5]). The subgroups assessed will be the same as sections 8.6.1 − 8.6.3 (age cohort, baseline HbA1c cohort (HbA1c at baseline of ≥ 7.5%. yes/no), etc.)

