8.6.4.1 Late Bolus Meal Challenge Safety and CGM Subgroup Analysis

Two challenges are expected per subjects per treatment period for a total of four challenges, therefore agreement of outcomes will need to be assessed. For continuous outcomes, two sets of Pearson's correlation coefficients will be calculated to measure concordance: one restricted to each treatment period (higher range target and lower range target), and a single coefficient for all four challenges. For categorical outcomes, a Cohen's kappa statistic for agreement or a similarly appropriate statistic will be calculated and presented to describe agreement/dependence of outcomes by individual subjects. Results will be compared by treatment period and across treatment periods.

The analyses described in sections 8.6.1, 8.6.2, and 8.6.3 will be repeated for subjects included in the late bolus meal challenge set. For the CGM outcomes, the mean of the CGM metrics for the two late meal

bolus challenges within study period will be used to account for within-subject non-independence (i.e. one data value per subject per study period).

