8.6.4.2 Time to Intervention Analysis

1005

1006

1007

1018

1031

1032

1033

1039 1040

1041

Time to intervention for both hypo- or hyperglycemia during the study meal challenge periods will be 1008 summarized. Time to intervention is defined as the time (in minutes) from start of meal until the first 1009 treatment is given as defined in Section 6.2. If multiple interventions are needed to treat hypo- or 1010 hyperglycemia during the meal challenge, only time to the earliest intervention will be summarized. The 1011 results will be presented using general summary statistics, as well as utilizing Kaplan-Meier time-to-event 1012 analysis where subjects who complete the meal challenge without requiring any intervention will be right-1013 censored. A cox proportional hazards model will be fit comparing time to intervention between the two 1014 active treatment periods. A p-value from the log-rank test will be used to evaluate whether there is 1015 evidence of a difference between the two target ranges with respect to time to intervention. Results will be 1016 compared by treatment period and across treatment periods. 1017

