8.8 Protocol Adherence and Retention

1044

1075	8.13 Subgroup Analyses
1076 1077	Results will be tabulated according to age cohort, baseline HbA1c category, and target activity use (standard target, lower target, sleep activity, exercise activity). There is an enrollment goal of at least half
1078 1079	of all participants in each age group have an HbA1c at baseline of \geq 7.5%, and all participants meeting that criteria will be analyzed as a subgroup.
1080	8.14 Multiple Comparison/Multiplicity
1081	There are no adjustments performed for multiple comparisons.
1082	8.15 Handling of Missing Data
1083 1084	All practical monitoring and follow-up steps will be taken to ensure complete and accurate data collection. All analyses will be based on available data only; no imputation for missing data is planned.
1085	8.16 General Statistical Considerations
1086 1087 1088	Up to six sites in the US will enroll subjects into the study. For the purposes of statistical analyses and data summaries, data from all study centers will be pooled. Not official assessment of poolability will be performed.
1089 1090 1091 1092 1093 1094	Unless otherwise specified, continuous variables will be summarizing using count, mean, median, standard deviation, and range. 95% confidence intervals, and/or first and third quartile may be presented were appropriate. Categorical variables will be summarized using count and percent of each level of categorical variable. Any statistical testing will be performed at a two-sided significance level of 5% with no adjustment for multiple testing. If the observed data are found not to follow a normal distribution, non-parametric methods may be employed (such as Wilcoxon rank sum test as appropriate).
1095 1096 1097	The statistical software package SAS® 9.3 or later will be used for all data derivations, summaries, listings, and statistical analyses. Additional statistical software may be used for graphics or validation purposes as appropriate.

1098	Chapter 9: Data Collection and Monitoring
1099	9.1 Case Report Forms and Other Data Collection

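### Section 8.6.4.2 names an ordinary log-rank test for times that the same participants contribute at both targets, without stating the unit of analysis or how repeated challenges are handled

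*Combined protocol and SAP*

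**What the plan says.** Section 8.6.4.2 plans Kaplan-Meier summaries of time to first intervention in the meal challenges, then two comparative analyses. The first is a model: "A cox proportional hazards model will be fit comparing time to intervention between the two" treatment periods. The second is a test: "A p-value from the log-rank test will be used to evaluate whether there is" a difference between the target ranges. It names no clustering, frailty, pairing or strata. It speaks of censoring subjects who finish a challenge without intervention, although each subject has several challenges.

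Section 8.6.4.1 gives the repetition: "Two challenges are expected per subjects per treatment period for a total of four challenges". It recognises that outcomes within a subject may agree, plans correlation and kappa statistics to describe this, and gives one device for dependence: "For the CGM outcomes, the mean of the CGM metrics for the two late meal" bolus challenges in a period is used, so that each subject has one value per period. That device is limited to CGM outcomes.

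Section 8.1 makes a general commitment: "The correlated nature of data collected by the same subject across multiple conditions will be accounted for in the statistical modeling". Its only example is a paired t-test for continuous outcomes. Section 8.2 says that p-values will be calculated but not used for formal inference. Section 8.16 adds: "Any statistical testing will be performed at a two-sided significance level of 5" percent, unadjusted.

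**The concern.** The ordinary log-rank test and the default Cox variance assume independent observations. Here one person's challenges fall on both sides of the comparison, two on each. The general commitment in 8.1 and the test named in 8.6.4.2 do not fit together. A paired t-test cannot be applied to censored times, and censored times cannot simply be averaged as the CGM metrics are. The phrase in 8.1 about multiple conditions also does not clearly reach two challenges at one target. A programmer who follows 8.6.4.2 to the letter would run the ordinary test.

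At stake are the standard error and p-value for whether the lower target changes how soon participants need treatment for low or high glucose. That is a safety-related question, though a secondary and exploratory one.

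**Working it through.** The documents give no event rate, hazard ratio, power or standard error for this analysis, so there is no planned figure to reproduce.

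**Inputs from the documents.**
- 72 completers (synopsis: "so that at least 72 complete the study"), 12 of them aged 2-5.
- Two challenges at each of two targets: 72 × 4 = 288 challenges, 72 × 2 = 144 per target.
- Window of 300 minutes, or 180 minutes for ages 2-5 (8.6.4: "start of meal through 5 hours from meal imitation [3 hours for age 2-5").
- Two-sided 5% level (8.16).

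**Assumptions not in the documents.** Constant hazard within a challenge; 20% or 50% of challenges with an intervention over 300 minutes; gamma frailty with variance 0 to 2 shared by all four challenges, and 0 to 1 specific to a participant's period; hazard ratio 0.6 for power. There were 2,000 runs per setting, so the Monte Carlo error at 5% is √(0.05 × 0.95 / 2000) = 0.5 points.

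**Formulas.** With Z = 1 for one target and z̄ the share of challenges at risk that have Z = 1, the log-rank score is U = Σ(Z − z̄) over events, and its ordinary variance is V = Σ z̄(1 − z̄). The clustered variance is V_R = Σ_i(Σ_j r_ij)², where r_ij is the score residual of challenge j in participant i. The tests are U/√V and U/√V_R.

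**Why the direction is not fixed.** Let each challenge's contribution have variance σ², with correlation ρ_w between two challenges in the same period and ρ_b between challenges in different periods. One participant's target contrast, (r1 + r2) − (r3 + r4), has variance 4σ² + 4ρ_wσ² − 8ρ_bσ² = 4σ²(1 + ρ_w − 2ρ_b). Independence gives 4σ².
- Correlation shared equally (ρ_w = ρ_b = ρ): ratio 1 − ρ, so the ordinary variance is too large.
- Correlation only within a period (ρ_b = 0): ratio 1 + ρ_w, so it is too small.

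**Type I error at nominal 5%, two challenges per period.** Each cell gives ordinary log-rank / clustered score test / log-rank stratified by participant.

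| Frailty variance | 20% events | 50% events |
|---|---|---|
| None | 5.4 / 4.8 / 5.4 | 4.6 / 5.1 / 5.6 |
| Shared 0.5 | 3.9 / 5.2 / 5.4 | 2.8 / 4.6 / 5.2 |
| Shared 1 | 3.4 / 4.8 / 5.1 | 1.4 / 5.1 / 5.4 |
| Shared 2 | 2.4 / 4.6 / 4.8 | 0.2 / 4.6 / 5.0 |
| Within period 0.5 | 6.8 / 5.1 / 6.6 | 7.8 / 5.1 / 7.8 |
| Within period 1 | 7.4 / 5.4 / 8.3 | 8.4 / 4.6 / 9.4 |
| Both, 1 and 1 | 5.9 / 5.2 / 9.6 | 6.7 / 5.8 / 11.7 |

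The simulated spread of U/√V agrees with the variance argument. Its standard deviation is 0.67 for shared variance 2 and 1.15 for within-period variance 1, both at 50% events. The second implies a rejection rate of 2[1 − Φ(1.96/1.15)] = 2[1 − Φ(1.70)], about 9%, against 8.4% simulated.

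**Power at hazard ratio 0.6, shared frailty 0.5 / 1 / 2.** At 50% events the ordinary test has 71% / 63% / 41%, against 76% / 75% / 71% for the clustered test. At 20% events it has 36% / 33% / 27%, against 38% / 35% / 34%.

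**One challenge per period.** The ordinary test rejects 0.4% to 5.8% of the time and the clustered test 3.6% to 5.6%. Reducing the data to one challenge per target therefore does not cure the pairing problem.

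**The case against.** The strongest reply is that the plan already covers this. Section 8.1 commits to modelling within-subject correlation and offers the paired t-test only as an example. Section 8.6.4.1 acknowledges dependence among the four challenges. A Cox model with clustered variance would still be the model that 8.6.4.2 names. This part stands. A reader might infer that the plan treats challenges as independent, but no section says so. What remains is a missing specification, plus one named test that, in its ordinary form, does not honour 8.1.

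Four other inferences go further than the documents allow:
- *The test is always conservative.* This holds only if correlation is shared about equally by all four challenges. Use of the same meal throughout (5.1.1) favours that pattern. A common target, a common two-week window and adjustable pump settings (3.7) favour within-period correlation.
- *Stratifying by participant would do as well.* It leaves within-period clustering in place: type I error was 6.6% to 11.7% in the last three rows of the table.
- *The Kaplan-Meier bands would be too narrow.* Section 8.6.4.2 promises no bands, 8.16 says only that intervals may be presented, and the unit of analysis is not stated.
- *A period term is required.* Section 8.1 openly assumes no period or carryover effects for exploratory purposes, and this point does not depend on challenging that.

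It is also fair to say that every size above rests on assumed inputs. At the mildest shared frailty with 20% events the effect is small: 3.9% against 5%, and power of 36% against 38%. The sample size was not set on statistical grounds (8.3), so no planned power is lost.

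**Conclusion.** The point holds as a specification gap with a named test that does not suit the design. If the ordinary log-rank test is run on all challenges, its p-value is miscalibrated and the sign of the error cannot be known in advance. Under the assumed event rates and frailties, type I error is 0.2% to 3.9% with correlation shared across the four challenges, and 6.8% to 8.4% with correlation within a period. The two can partly offset each other (5.9% and 6.7% with both). The participant-clustered test stayed between 4.6% and 5.8% throughout. The default Cox standard error has the same weakness, but the Cox model can be kept with a different variance.

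The consequence is limited. This is a secondary endpoint, 8.2 rules out formal inference from the p-values, and the primary safety endpoints are untouched. It should be corrected before analysis because the correction is nearly free.

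**What to change.** Add to 8.6.4.2, in substance: each meal challenge is one observation; the Cox model for target uses a robust sandwich variance clustered on participant; its robust score (or Wald) test is reported in place of the ordinary log-rank p-value. Add a cross-reference showing that this is how 8.1 is carried out for censored times. Do not rely on stratification by participant alone. The Kaplan-Meier curves can stay as description.

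Use the same clustered variance for any comparison of late bolus with normal bolus, which is also within-person. That is the contrast named in secondary endpoint 8, whereas 8.6.4.2 tests only the targets; this mismatch is a separate matter to reconcile.

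The cost is two or three sentences in the plan and a routine option in the Cox procedure. Data collection, visits and sample size do not change.

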8.6.4.3 Number of interventions analysis

Number of interventions for hypo- or hyperglycemia during the study meal challenge periods will be summarized both overall and by type. The results will be presented using general summary statistics.

Type of intervention may include timing of intervention (during meal, less than one hour after starting meal, greater than one hour after meal start), the number of carbs administered (grouped in increments of 10 grams), and the timing of carb administration (less than 15 minutes per administration vs 15 minutes or more). The categories and groupings utilized for intervention type will be expanded or decreased based on the types of interventions that actually occur in the study. Results will be compared by treatment period and across treatment periods.

Type of intervention will be reviewed and assessed by the study Medical Monitor prior to analysis to define the logic that can be applied across all subjects (e.g., an intervention that occurred more than 15 minutes after the previous intervention will count as new intervention). Different logic may be applied to different age cohorts. This logic will be fully detailed in the final clinical study report.

8.7 Intervention Adherence

The following tabulations will be performed:

- Sensor use percent time of use as a function of overall treatment period
- Sensor use is defined as percent of time CGM is recorded as active (to include warmup) vs total study time.
- Closed loop system use percent time of use as a function of overall treatment period
- Closed loop system use is defined as percent of time closed-loop is recorded as active (to include pinning in sensor warmup) vs total study time.
 - Percent time in different operational modes as a function of overall treatment period
 - The investigational device allows for the following operational modes: standard target, lower target, sleep activity, and exercise activity.

For intervention adherence, overall treatment period is calculated from the start of the treatment period to the end of the treatment period where any gaps in CGM data are ignored.

1045	The following tabulations and analyses will be performed to assess protocol adherence for the study:
1046 1047	 Number of protocol deviations by site and by type, and number of unique subjects with each type of protocol deviation
1048	• Disposition summary (e.g., chart, table) accounting for all enrolled participants at each scheduled visit
1049	 Number of and reasons for unscheduled visits and phone calls
1050	• Number of participants who were enrolled but did not enter the Treatment Period and reasons
1051	 Number of participants who stopped treatment and reasons
1052	8.9 Baseline Descriptive Statistics
1053 1054 1055	Baseline demographic and clinical characteristics of the cohort of participants who initiate the Treatment Period will be summarized in a table using summary statistics appropriate to the distribution of each variable. Descriptive statistics will be displayed by treatment group for the following:
1056	• Age
1057	• Sex
1058	• Race
1059	• Ethnicity
1060	 Socio-economic factors (income, education, and/or insurance status)
1061	• Diabetes duration
1062	• HbA1c
1063	• BMI
1064	Total daily insulin
1065	• Prior severe hypoglycemia and DKA events in the last 6 months
1066	8.10 Additional Tabulations and Analyses
1067	The following data will be tabulated at baseline, for the run-in period, and for the two treatment periods.
1068 1069	• Insulin metrics (units/kg): total daily insulin, total daily basal insulin, total daily bolus insulin (plus total daily manual bolus, total daily automated bolus)
1070	8.11 Device Issues
1071	The following tabulations will be performed with respect to device issues:
1072	• Number of device issues by type, and number of unique subjects with each type of device issue
1073	8.12 Planned Interim Analyses
1074	No formal interim analyses are planned.

8.8 Protocol Adherence and Retention

1044

1075	8.13 Subgroup Analyses
1076 1077	Results will be tabulated according to age cohort, baseline HbA1c category, and target activity use (standard target, lower target, sleep activity, exercise activity). There is an enrollment goal of at least half
1078 1079	of all participants in each age group have an HbA1c at baseline of \geq 7.5%, and all participants meeting that criteria will be analyzed as a subgroup.
1080	8.14 Multiple Comparison/Multiplicity
1081	There are no adjustments performed for multiple comparisons.
1082	8.15 Handling of Missing Data
1083 1084	All practical monitoring and follow-up steps will be taken to ensure complete and accurate data collection. All analyses will be based on available data only; no imputation for missing data is planned.
1085	8.16 General Statistical Considerations
1086 1087 1088	Up to six sites in the US will enroll subjects into the study. For the purposes of statistical analyses and data summaries, data from all study centers will be pooled. Not official assessment of poolability will be performed.
1089 1090 1091 1092 1093 1094	Unless otherwise specified, continuous variables will be summarizing using count, mean, median, standard deviation, and range. 95% confidence intervals, and/or first and third quartile may be presented were appropriate. Categorical variables will be summarized using count and percent of each level of categorical variable. Any statistical testing will be performed at a two-sided significance level of 5% with no adjustment for multiple testing. If the observed data are found not to follow a normal distribution, non-parametric methods may be employed (such as Wilcoxon rank sum test as appropriate).
1095 1096 1097	The statistical software package SAS® 9.3 or later will be used for all data derivations, summaries, listings, and statistical analyses. Additional statistical software may be used for graphics or validation purposes as appropriate.

1098	Chapter 9: Data Collection and Monitoring
1099	9.1 Case Report Forms and Other Data Collection
1100 1101 1102 1103 1104 1105	The main study data are collected on electronic case report forms (eCRFs). When data are directly collected in electronic case report forms, this will be considered the source data. For any data points for which the eCRF is not considered source (e.g. lab results that are transcribed from a printed report into the eCRF, data collected in the electronic medical record, study specific source worksheets, etc.), the original source documentation will be maintained in the participant's study chart or medical record. This source must be readily verifiable against the values entered into eCRF.
1106 1107	Electronic device data files are obtained from the study software and individual hardware components. These electronic device files are considered the primary source documentation.
1108	9.2 Study Records Retention
1109 1110 1111	Each participating site will maintain appropriate medical and research records for this trial, in compliance with GCP and regulatory and institutional requirements for the protection of confidentiality of participants.
1112 1113 1114 1115 1116 1117	Study documents should be retained for a minimum of 2 years after the last approval of a marketing application in an ICH region and until there are no pending or contemplated marketing applications in an ICH region or until at least 2 years have elapsed since the formal discontinuation of clinical development of the investigational product. These documents should be retained for a longer period, however, if required by local regulations. No records will be destroyed without the written consent of the sponsor, if applicable. It is the responsibility of the sponsor to inform the investigator when these documents no longer need to be retained.
1119	9.3 Quality Assurance and Monitoring
1120 1121 1122 1123 1124 1125	Designated personnel from the Coordinating Center will be responsible for maintaining quality assurance (QA) and QC systems to ensure that the clinical portion of the trial is conducted and data are generated, documented and reported in compliance with the protocol, GCP and the applicable regulatory requirements, as well as to ensure that the rights and wellbeing of trial participants are protected and that the reported trial data are accurate, complete, and verifiable. Adverse events will be prioritized for monitoring.
1126 1127 1128 1129	A monitoring plan will be developed and revised as needed during the course of the study. Study conduct and monitoring will conform with 21 Code of Federal Regulations (CFR) 812. This plan will describe in detail who will conduct the monitoring, at what frequency monitoring will be done, at what level of detail monitoring will be performed, and the distribution of monitoring reports.
1130 1131 1132 1133	The data of most importance for monitoring at the site are participant eligibility and adverse events. Therefore, the monitoring plan will focus on these areas. As much as possible, remote monitoring will be performed in real-time with on-site monitoring performed to evaluate the verity and completeness of the key site data. Elements of the monitoring may include:

1134	•	Qualification	assessment,	training,	and	certification	for s	sites a	nd site	personnel
------	---	---------------	-------------	-----------	-----	---------------	-------	---------	---------	-----------

- Oversight of Institutional Review Board (IRB) coverage and informed consent procedures
- Central (remote) data monitoring: validation of data entry, data edits/audit trail, protocol review of entered data and edits, statistical monitoring, study closeout
- On-site monitoring (site visits): source data verification, site visit report
- Agent/Device accountability
- Communications with site staff
- Patient retention and visit completion
- Quality control reports
- Management of noncompliance
- Documenting monitoring activities
- Adverse event reporting and monitoring
- 1146 Coordinating Center representatives or their designees may visit the study facilities at any time in order
- to maintain current and personal knowledge of the study through review of the records, comparison
- with source documents, observation and discussion of the conduct and progress of the study.
- The investigational site will provide direct access to all trial related source data/documents, and reports
- for the purpose of monitoring and auditing by the sponsor, and inspection by local and regulatory
- 1151 authorities.

1152

1162

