8.6.3 Analysis of CGM Endpoints

CGM metrics will be assessed in CGM analysis set, and computed for the Run-In and both Treatment Periods separately. CGM metrics will be computed per subject over 24 hours, during daytime (6am-11:59pm), and during nighttime (12am-5:59am), as well as by age cohort (adults/adolescents, children 6 – 13, and preschool), baseline HbA1c cohort (HbA1c at baseline of ≥ 7.5%,yes/no), and target activity use as specified by the device (standard target, lower target, sleep activity, and exercise activity). The main statistical comparison will be made between the three 2-week periods (Run In, Treatment

The main statistical comparison will be made between the three 2-week periods (Run In, Treatment Period at standard target, Treatment Period at lower target). The comparison will be pairwise – Run-in vs standard targe, Ru-in vs lower target, and standard vs lower target. The percent time in glycemic ranges will be calculated as the number of measurements in the specified range divided by the total number of measurements for which it can be determined whether or not the measurement was in specified range.

The "Low" and "High" CGM readings will be included in all analyses. Percent time will be compared using a paired t-test assuming sufficient normality assumptions hold, otherwise an appropriate non-parametric method will be utilized.

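### The plan's one named non-parametric fallback, the Wilcoxon rank-sum test, is for independent samples, while every CGM between-period contrast is within participant; a paired rank test should be named instead.

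*Combined protocol and SAP*

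**What the plan says.** - **Contrasts (8.6.3).** "The main statistical comparison will be made between the three 2-week periods (Run In, Treatment" Period at each of the two targets), taken pairwise: run-in vs standard, run-in vs lower, standard vs lower. All participants are meant to pass through all three periods, so each contrast is within participant.
- **Main test (8.6.3).** Percent time is compared "using a paired t-test assuming sufficient normality assumptions hold"; "otherwise an appropriate non-parametric method will be utilized". That method is not named.
- **General rule (8.1).** For continuous variables "distributions will be tested for the normality assumption"; if parametric methods prove inadequate, "an appropriate non-parametric technique will be used", again unnamed. The same section adds: "The correlated nature of data collected by the same subject across multiple conditions will be accounted for in the statistical modeling", with the paired t-test as its example.
- **General rule restated (8.16).** If the observed data are not normal, "non-parametric methods may be employed (such as Wilcoxon rank sum test as appropriate"). This is the only alternative to the t-test that the plan names. The log-rank test in 8.6.4.2 serves time to intervention and does not fill the gap.
- **Status of the results.** % time <54 and <70 mg/dL are secondary endpoints (8.4). P-values are calculated at a two-sided 5% level without adjustment (8.16), but 8.2 says they do not support formal inference.

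**The concern.** Someone programming the analysis who looks up the fallback finds one named test, and it treats two periods in the same people as two separate samples. That does not fit the design and conflicts with the commitment in 8.1.

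Two features make this more than cosmetic. First, % time <54 and <70 mg/dL are bounded at zero and plausibly skewed, so they are the endpoints most likely to reach the fallback. Second, 8.1 and 8.16 describe the normality check in terms of the variables or the observed data. What a paired t-test needs is approximate normality of the within-participant differences, and skewed outcomes in both periods do not by themselves show that this fails.

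With positive within-person correlation, an unpaired test on paired data rejects too rarely. For hypoglycemia that is the unhelpful direction: a modest rise at the lower target could carry an unremarkable p-value.

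**Working it through.** **Inputs from the documents.** Completers: 30 + 30 + 12 = 72 (8.3). Two-sided 5% level, no adjustment (8.16). The plan gives no power figure, SD, effect size or within-person correlation, so there is no figure of its own to reproduce.

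**Assumptions.** Within-person correlation ρ from 0.3 to 0.8; log-normal % time with median 0.8% and log-SD 1.0, rounded to 0.025%; increases of 1.25-, 1.5- and 2-fold.

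**Step 1: normal approximation.** Let σ be the SD in each period, with n pairs. An unpaired statistic divides the mean difference by σ√(2/n), but its true standard error is σ√(2(1−ρ)/n). Under no difference the statistic therefore has SD √(1−ρ), and

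- true type I error = 2Φ(−1.96/√(1−ρ));
- power at the shift where the paired test has 80% = Φ(1.96 + 0.84 − 1.96/√(1−ρ)).

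The sample size cancels from both.

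| ρ | 1.96/√(1−ρ) | True type I error | Power when the paired test has 80% |
|---|---|---|---|
| 0.3 | 2.34 | 1.9% | 68% |
| 0.5 | 2.77 | 0.56% | 51% |
| 0.7 | 3.58 | 0.035% | 22% |

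**Step 2: simulation of the two rank tests** (2,000 to 3,000 runs per cell). Entries are rejection rates in %, rank-sum / signed-rank.

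| n | ρ | No change | 1.25-fold | 1.5-fold | 2-fold |
|---|---|---|---|---|---|
| 72 | 0.3 | 1.5 / 4.2 | 20.7 / 28.4 | 69.3 / 74.2 | 99.1 / 99.0 |
| 72 | 0.5 | 0.5 / 5.2 | 17.5 / 39.2 | 71.8 / 86.9 | 99.7 / 99.9 |
| 72 | 0.7 | 0.1 / 5.5 | 13.4 / 57.4 | 76.4 / 97.3 | 100 / 100 |
| 30 | 0.3 | 2.2 / 5.2 | 9.1 / 13.9 | 29.7 / 37.4 | 77.1 / 81.5 |
| 30 | 0.5 | 0.3 / 4.2 | 5.3 / 16.9 | 25.7 / 47.7 | 78.9 / 90.6 |
| 30 | 0.7 | 0.1 / 4.4 | 3.1 / 28.7 | 24.0 / 70.0 | 83.9 / 98.6 |
| 12 | 0.5 | 0.9 / 4.7 | 3.1 / 11.3 | 8.8 / 21.8 | 32.4 / 51.4 |
| 12 | 0.7 | 0.2 / 4.7 | 1.5 / 14.6 | 5.4 / 33.1 | 27.1 / 70.3 |

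At increases where the signed-rank test has about 80% power with 72 pairs, simulated rank-sum power is 75% (ρ 0.3), 62% (0.5), 51% (0.6), 33% (0.7) and 11% (0.8). The loss is milder than in Step 1 but has the same shape.

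**Step 3: sensitivity to spread.** With log-SD 0.9 the pattern holds. Type I error at n=72, ρ 0.5 is 0.7%. Power for a 1.5-fold rise at n=30, ρ 0.7 is 32% (rank-sum) vs 79% (signed-rank). At n=72, rank-sum power for a 1.5-fold rise is 77 to 87%.

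**Step 4: comparison with the test being replaced.** At n=72, ρ 0.7 and a 1.25-fold rise (log-SD 1.0), the paired t-test rejects in 40.2% of runs and the rank-sum test in 13.4%. Switching to the rank-sum would then lose power against the test set aside as inadequate; the signed-rank gains (57.4%).

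**The case against.** **The rank-sum test is not assigned to these endpoints.** A reader might infer that it is the prespecified fallback for hypoglycemia. The documents do not support that. The 8.16 wording is permissive and general, 8.6.3 asks only for a suitable method, and 8.1 requires the correlation to be respected. Read together, a careful analyst would choose a paired test. This stands, and it makes the consequence conditional. It does not remove the mismatch, since the only test named is the one that 8.1 would rule out for these contrasts.

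**Most misses are not due to the choice of test.** For a 1.25-fold rise the signed-rank test is itself weak: it misses about 61% at n=72, ρ 0.5 (100 − 39.2) and about 85% at n=12, ρ 0.7 (100 − 14.6). The sample size was not chosen for power (8.3). This stands.

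**The model is simple.** It has no separate point mass at zero. Exact zeros and ties affect both tests, and the documents give no data on them. The power figures are therefore illustrative; the direction of the error does not depend on them.

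**The normality wording may be harmless.** In 8.6.3 the check is attached to the paired t-test, whose assumption concerns the differences. That is a fair reading, so this part is a clarification.

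**Little hangs on the p-value.** The endpoints are secondary, p-values are exploratory, the primary safety endpoints are untouched, and means and medians are reported anyway. This stands and limits the severity.

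**Conclusion.** The mismatch is real. The one named rank alternative to the t-test assumes independent samples, the period contrasts are paired, and no paired rank test appears in the plan. If the example were followed with 72 pairs, true type I error would be about 2% at correlation 0.3 (1.5% simulated, 1.9% by approximation), 0.5 to 0.7% at 0.5, and at most about 0.1% at 0.7. Power for modest increases would fall, most at high correlation and in the cohorts of 30 and 12.

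A reader might go further and conclude that the fallback would miss most real increases in hypoglycemia. That does not follow. Relative to a paired test with 80% power, the rank-sum misses more than half only when the correlation exceeds about 0.5 (approximation) to 0.6 (simulation). With 72 pairs it still has 69 to 76% power for a 1.5-fold rise (log-SD 1.0) and at least 99% for a doubling, at correlations 0.3 to 0.7.

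The sizes rest on assumed log-normal data, spread and correlation. With secondary endpoints and exploratory p-values, this should be fixed but is not a must-fix.

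**What to change.** 1. In 8.16, for between-period contrasts, replace the rank-sum example with the Wilcoxon signed-rank test on within-participant differences. The rank-sum can remain for any comparison of separate groups of participants.
2. In 8.6.3, name the same test as the fallback, optionally with a Hodges-Lehmann estimate and 95% confidence interval. Section 8.6.4.1 repeats the 8.6.3 analyses for the meal challenges, so the change carries over.
3. In 8.1, 8.6.3 and 8.16, state that normality is assessed on the within-participant differences.
4. Optional: fix the rank method in advance for named endpoints, such as % time <54 and <70 mg/dL, so that the choice does not depend on the observed data.

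The cost is SAP wording only. No data, visits or sample size change.
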